10.5 Appendix 5: Censoring rules

Table 5.1 Censoring Rules for PFS, DOR & DDC Based on Food & Drug Administration (FDA) Guidelines

For calculation of 2 or more missed consecutive scheduled assessments, see the text after the censoring rules tables.

If a subject met multiple censoring criteria, the earliest censoring date will be used.

Situation (Censoring Order)	Date Patient Has Event or is Censored	Situation Outcome
Inadequate baseline assessment* (1)	Randomization date	Censored
Inadequate post-baseline assessments* (2)	Randomization date	Censored
* Not applicable to DOR and DCR		
Progression documented on or between scheduled tumor assessments	Date of first objective tumor assessment showing objective progression	Progressed (Event)
Progression documented not after 2 or more missed consecutive scheduled assessments during the treatment period or not after 1 or more missed scheduled assessments during the Follow-up period	For RECIST 1.1, the Date of objective progression / for iRECIST, the date of iUPD if progression associated with that iUPD has been confirmed.	Progressed (Event)
Death (and progression has not occurred previously) not after 2 or more missed consecutive scheduled assessments during the treatment period or not after 1 or more missed scheduled assessments during the Follow-up period	Date of death	Death (Event)

Statistical Analysis Plan (SAP) BNT111-01

Page 71 of 78 Version: Final v7.0 Date: 05Mar2024

Situation (Censoring Order)	Date Patient Has Event or is Censored	Situation Outcome
Death without objective progression	Date of death	Death (Event)
Death or progression after 2 or more consecutive missing scheduled assessments during the treatment period or after 1 or more missed scheduled assessments during the Follow-up period (3)	Date of last adequate assessment with evidence of no progression; if no adequate assessment exists then censored at the randomization date.	Censored
New anti-cancer therapy started prior to progression or death (4)	Date of last adequate assessment with evidence of no progression before anti-cancer therapy; if no adequate assessment exists then censored at the randomization date	Censored
No progression or death (6)	Date of last adequate assessment with evidence of no progression; if no adequate assessment exists then censored at the randomization date	Censored
Treatment discontinuation for undocumented progression (this reason would be assumed if for the end of treatment (EOT) CRF page "Other" has been ticked and details are "clinical progression") (5)	Date of last objective tumor assessment prior to treatment discontinuation For DOR & DDC: Apply censoring on Day 1, if no post-baseline assessment available meeting objective response (for DOR) or disease control (for DDC) up to EOT with qualifying reasons of treatment discontinuation	Censored

Statistical Analysis Plan (SAP) BNT111-01

Page 72 of 78 Version: Final v7.0 Date: 05Mar2024

Situation (Censoring Order)	Date Patient Has Event or is Censored	Situation Outcome
Treatment discontinuation due to toxicity (due to an adverse event that is related to IMP ie BNT111 or Cemiplimab) or for the 'other' category on the CRF (7) with a documented disease progression	Date of first documented progression including protocol specified assessments continued through follow-up period	Event
Treatment discontinuation due to toxicity (due to an adverse event that is related to IMP ie BNT111 or Cemiplimab) or for the 'other' category on the CRF (8) without documented disease progression	Date of last objective tumor assessment including protocol specified assessments continued through follow-up period	Censored
Lost to follow-up (9)	Date of last adequate assessment with evidence of no progression; if no adequate assessment exists then censored at the randomization date.	Censored

Page 73 of 78 Version: Final v7.0 Date: 05Mar2024

Method for determining if 2 or more consecutive tumor assessments have been missed.

- 1. Subject has 1 consecutive missed response assessments = subject has more than 6*7+7+7 days between actual consecutive response assessments for 3 months or 9*7+7+7 for next 9 months or 12*7+14+14 thereafter
- 2. Subject has 2 consecutive missed response assessments = subject has more than 2*6*7+7+7 days between actual consecutive response assessments for 3 months or 2*9*7+7+7 for next 9 months or 2*12*7+14 + 14 thereafter

If the missing assessments are in the first 3-month period and there are assessments present after the first 3 months then the following is done:

- 1. Subject has week 12 response assessment missing = subject has more than 9*7+7+7 days between actual consecutive response assessments

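### SAP Table 5.1 (PFS, DOR, DDC) both counts and censors a death after missed scans, has no missed-scan count for deaths, and has no limit bridging the 9-to-12-week change in scan interval

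*SAP*

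**What the plan says.** All of this is in SAP section 10.5 (Appendix 5), unless stated otherwise.

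- **Row 3** censors, at the last adequate scan without progression, "Death or progression after 2 or more consecutive missing scheduled assessments during the treatment period or after 1 or more missed scheduled assessments" in the follow-up period.
- **Conditional death row (unnumbered, event):** "Death (and progression has not occurred previously) not after 2 or more missed consecutive scheduled assessments during the treatment period", and not after one or more missed scans in follow-up.
- **Unconditional death row (unnumbered, event):** "Death without objective progression", dated at death, with no missed-scan condition.
- **Several criteria met:** "If a subject met multiple censoring criteria, the earliest censoring date will be used". The table also gives order numbers in its first column.
- **Counting note:** one or two missed scans are inferred from the number of days between actual consecutive response assessments. There are separate limits for the 6-, 9- and 12-week periods and a special rule for gaps that start in the first 3 months and end later.
- **Definitions:** SAP 8.4.2.5 (PFS) and 8.4.2.3 (DOR) both count death from any cause. SAP 8.1 and the protocol (9.4.1, 9.4.3) leave the detailed censoring rules to this table.

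**The concern.** These rules decide whether a patient contributes an event or a censored time, and on which day. In three places they do not give one correct answer: a death after missed scans, the count of missed scans before a death, and a scan gap that crosses month 12. In the first two, two programmers could follow the SAP and report different outcomes for the same patient. In the third, the stated limits can count scans as missed that were not, and so censor real progressions. The trial is open-label, so a reading chosen after the data are seen would weaken prespecification of PFS and DOR.

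**Working it through.** **1. Death rows side by side.** The conditional death row and row 3 are exact complements: not after missed scans is an event, after missed scans is censored. The unconditional row therefore duplicates the first or contradicts the second. The earliest-date sentence ranks censoring criteria against each other; it cannot decide event versus censored.

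Example: a patient is in follow-up after an investigator's decision to stop, with no new therapy. The week 21 scan (day 148) is clean, week 30 is missed, and death occurs in week 36 (36×7+1 = day 253). The unconditional row gives an event on day 253. If week 30 counts as missed, row 3 censors at day 148, which is 253−148 = 105 days earlier.

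**2. Does week 30 count as missed?** Read literally, the method needs a later response assessment. There is none, so there is no count and row 3 cannot be triggered. If the death date is used as the end of the gap, 105 days exceeds 77 but not 140, so one scan is missed and row 3 applies. The SAP states neither reading.

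**3. Scan-gap limits.**

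Inputs: target days from SAP Appendix 7 (week 6 = 43, 12 = 85, 21 = 148, 30 = 211, 39 = 274, 48 = 337, 60 = 421, 72 = 505). Windows from SAP Table 3.2: ±7 days in the 6- and 9-week periods, ±14 in the 12-week period.

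The SAP's limits follow one formula: the longest gap compatible with k missed scans is the scheduled gap plus the window at each end.

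- One missed if more than: 6×7+14 = 56; 9×7+14 = 77; 12×7+28 = 112.
- Two missed if more than: 2×6×7+14 = 98; 2×9×7+14 = 140; 2×12×7+28 = 196.
- 6-to-9-week bridge: 9×7+14 = 77 (week 12 missed); 6×7+9×7+14 = 119 (two missed).

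These reproduce the SAP. The bridge is needed: missing only week 12 leaves 148−43 = 105 days, above 98 but below 119.

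The same test at the 9-to-12-week change, where the SAP has no bridge:

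| Gap (weeks) | Truly missed | Target gap (days) | Range with windows | By 9-week limits (77/140) | By 12-week limits (112/196) |
|---|---|---|---|---|---|
| 48–60 | 0 | 84 | 63–105 | one, if over 77 | none |
| 39–60 | 1 | 147 | 126–168 | two, if over 140 | one |
| 48–72 | 1 | 168 | 147–189 | two | one |
| 30–60 | 2 | 210 | 189–231 | two | one up to 196, else two |

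The SAP does not say which period's limit governs a gap crossing month 12 (12×30.4375 = 365.25 days).

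- **Only week 48 missed:** the start of the gap (day 274) and the missed visit (day 337) both lie before that point, so the 140-day limit is the natural one. An on-treatment progression at week 60 is then censored at day 274 instead of being an event on day 421.
- **Nothing missed, weeks 48–60:** the gap starts in the 9-week period, and 84 exceeds 77. In follow-up, where one missed scan is enough, progression in a compliant patient would be censored.
- Using the 12-week limits throughout is no cure: two truly missed scans (weeks 30–60, 189 to 196 days) would count as one.

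The missing limits by the SAP's own formula:

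- Weeks 48–60, none missed: 12×7+7+14 = 105.
- Weeks 39–60, one missed: 9×7+12×7+7+14 = 168.
- Weeks 48–72, one missed: 2×12×7+7+14 = 189.

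**The case against.** **Intent is clear enough.** The conditional death row and row 3 fit together, and a specific rule normally governs a general one. That is a fair guide to what was meant, but the SAP gives no precedence. The PFS definition in SAP 8.4.2.5 also points the other way, since it counts every death. Row 3 names deaths expressly, so the definition cannot quietly settle the matter.

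**A programmer would use the death date to close the gap.** That is reasonable but unwritten, and variants differ. After a day-85 scan, two missed scans could begin after day 211 (week-30 target), 218 (window closed) or 225 (85+140). A reader might infer that only deaths on days 212–225 are in doubt. As written, no count exists for any death.

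**The week-48 case is rare.** It needs a patient who is on treatment, progression-free at week 39, misses exactly one scan, has a gap over 140 days and progresses at week 60. This bears on frequency, not on whether the rule is right. The week 48–72 example is weaker, because the missed visit (day 421) falls in the 12-week period, where the 196-day limit would give one missed.

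**Stronger readings that the documents do not support:**

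- *The order numbers and the earliest-date sentence contradict each other.* Take a clean day-85 scan, a stop for clinical progression, a clean day-148 scan, then new therapy. Order would give day 148 (row 4); earliest date gives day 85 (row 5). But the earliest-date sentence is the only explicit date rule. SAP 8.1 requires reasons for censoring to be summarized, and the order can serve to choose that reason. This needs a clarifying sentence, no more.
- *Rows 2 and 8 turn deaths into censored times.* Neither row mentions death. SAP 8.4.2.5 (PFS) and Protocol 9.4.3 (PFS and DOR) limit censoring to patients alive without progression or lost to follow-up, which largely settles it. The DOR formula that uses only the progression date looks like a slip. Row 2 matters only if the analysis set, whose name is redacted, includes patients without a post-baseline scan.
- *"Progression documented on or between scheduled tumor assessments" conflicts with row 3 in the same way.* Its wording presupposes that the scheduled scans took place.

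**Conclusion.** Three defects stand: the unconditional death row conflicts with row 3; missed scans before a death have no count; and the 9-to-12-week change lacks the bridging limit that the SAP gives the 6-to-9-week change. They should be fixed because the rules are wrong or incomplete as written and the correction is cheap.

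Per patient the consequence can be large: event on day 253 or censored at day 148 in the follow-up death, and censored at day 274 instead of an event on day 421 in the week-48 case. These examples assume scans on the Appendix 7 target days and, for week 48, the 140-day limit.

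The overall effect on PFS, DOR and DDC cannot be sized. A reader might infer that correction would make PFS look worse. No direction is supported: removing the unconditional death row lets row 3 censor deaths, while the bridging limits restore progressions as events. PFS and DOR are secondary, DDC is exploratory, and all are descriptive. The ORR test does not use this table, and OS uses Table 5.2.

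**What to change.** In SAP Appendix 5:

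1. Delete the unconditional death row, or condition it to agree with row 3.
2. For deaths, count the scheduled scans due between the last adequate scan and death, and state whether a scan is due on its target day or when its window closes.
3. Add limits for gaps that cross the 9-to-12-week change, keyed to the last scan before the gap. After a week-48 scan: one missed if more than 105 days, two if more than 189. After a week-39 scan: two missed if more than 168 days.

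Minor tidy-ups:

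- State that the earliest date sets the censoring date and the order number only chooses the reported reason, or the reverse.
- Limit rows 2 and 8 to patients without a later death, in line with SAP 8.4.2.3 and 8.4.2.5 and Protocol 9.4.3.
- The footnote to rows 1 and 2 reads "Not applicable to DOR and DCR". The table covers DDC, and DCR is a rate with no censoring; correct it if DDC is meant.

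Cost: edits to one table and its counting note, with matching changes to the PFS, DOR and DDC derivations. Data collection does not change.

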10.6 Appendix 6: EORTC-QLQ-C30

Table 8.2 Scoring of QLQ-C30

	Scale	Number of items	Item range*	Version 3.0 Item numbers	Function scales
Global health status / QoL					
Global health status / QoL	QL	2	6	29, 30	
Functional scales					
Physical functioning	PF	5	3	1 to 5	F
Role functioning	RF	2	3	6, 7	F
Emotional functioning	EF	4	3	21 to 24	F
Cognitive functioning	CF	2	3	20, 25	F
Social functioning	SF	2	3	26, 27	F
Symptom scales / items					
Fatigue	FA	3	3	10, 12, 18	
Nausea and vomiting	NV	2	3	14, 15	
Pain	PA	2	3	9, 19	
Dyspnea	DY	1	3	8	
Insomnia	SL	1	3	11	
Appetite loss	AP	1	3	13	
Constipation	СО	1	3	16	
Diarrhea	DI	1	3	17	
Financial difficulties	FI	1	3	28	

^{*} Item range is the difference between the possible maximum and the minimum response to individual items; most items take values from 1 to 4, giving range = 3.

Page 76 of 78 Version: Final v7.0 Date: 05Mar2024

All of the scales and single-item measures range in score from 0 to 100. A high scale score represents a higher response level. Therefore, a high score for a functional scale represents a high/healthy level of functioning, a high score for the global health status / QoL represents a high QoL, but a high score for a symptom scale/item represents a high level of symptomatology / problems. The scoring procedure for each of the scales is the same and consists of computing the raw score (RS) and then computing the actual scale score (S) by making a linear transformation to standardize the score to values from 0 to 100 as shown below.

For all scales, the RawScore, RS, is the mean of the component items:

$$Raw\ Score = RS = \{I_1 + I_2 + \dots + I_n\}/n$$

Then for Functional scales:

$$Score = \left\{1 - \frac{RS - 1}{range}\right\} \times 100$$

and for Symptom scales / items and Global health status / QoL:

$$Score = \left\{ \frac{RS - 1}{range} \right\} \times 100$$

Where I_1 , I_2 , ... I_n are the individual items and Range is the difference between the maximum possible value of RS and the minimum possible value. The range of RS equals the range of the item values. Most items are scored 1 to 4, giving Range = 3. The exceptions are the items contributing to the Global Health Status / QoL, which are 7-point questions with Range = 6.

Missing items

Score will be derived if at least half of the items from the scale are not missing, otherwise it will be set to missing.

Page 77 of 78 Version: Final v7.0 Date: 05Mar2024

10.7 Appendix 7: Algorithm for visit window mapping of tumor assessments for depth of response

All data points for tumor assessments will be used. This section explains how to assign visits to the assessments for the depth of response analysis.

Data is collected by evaluation number. This evaluation number will be used to group assessments/records for same targeted visit. The tumor assessment data, including unscheduled visit data, will be mapped per the details described below:

Derive AVISIT1/AVISIT1N based on tumor assessment date.

- Calculate trial day of tumor scan performed referenced to first dose date.
- Define target assessment day and analysis window range (lower and upper limits) based on protocol specified schedule.
- Check where the calculated trial day falls and assign AVISIT1.
- AVISIT1N will represent week number of the derived visit (numeric part of AVISIT1).
- For the summary analysis by visit, the assessment closest to the target day will be analyzed. In case, 2 assessments are equidistant, the earliest assessment will be used in the analysis.

Some illustrative examples:

AVISIT1	AVISIT1N	AWTARGET1 (Analysis Window Target)	AWLO1 (Analysis Window Beginning Timepoint)	AWHI1 (Analysis Window Ending Timepoint)
Screening	0	-28	-28	-1
Week 6	6	43	1	63
Week 12	12	85	64	116
Week 21	21	148	117	179
Week 30	30	211	180	242
Week 39	39	274	243	305
Week 48	48	337	306	378
Week 60	60	421	379	462
Week 72	72	505	463	546
Week 84	84	589	547	630
Week 96	96	673	631	714
Week 108	108	757	715	798
Add-on Week 6	1006	43	1	63
Add-on Week 12	1012	85	64	116
Add-on Week 21	1021	148	117	179
Add-on Week 30	1030	211	180	242
Add-on Week 39	1039	274	243	305
Add-on Week 48	1048	337	306	378
Add-on Week 60	1060	421	379	462
Add-on Week 72	1072	505	463	546
Add-on Week 84	1084	589	547	630
Add-on Week 96	1096	673	631	714
Add-on Week 108	1108	757	715	798

Page 78 of 78 Version: Final v7.0 Date: 05Mar2024

10.8 Rules for assigning date of overall response from tumor assessment page

		Each Evaluation #		
Overall Timepoint Response	Overall Timepoint Response date	Target Lesion Date	Non-Target Lesion Date	New Lesion Date
PD	min(dt1, dt2, dt3)	dt1*	dt2*	dt3*
CR	max(dt1, dt2)	dt1	dt2	-
PR	dt1	dt1	any	-
SD (Not a CR, PR or PD)	min(dt1, dt2)	dt1	dt2	· _
NA, NE	min(dt1, dt2, dt3)	dt1	dt2	dt3

^{*} indicates a PD response by individual Target or Non-Target or appearance of New Lesion, otherwise corresponding date can be excluded while picking the earliest scan date.

Note: For BICR data, Non-CR/Non-PD and No Evidence of Disease responses can be present. The same rule as for SD will be followed.
